### 11.1.5. Statistical Analyses / Methods

Details of the planned displays are provided in [Appendix 12: List of Data Displays](#) and will be based on GSK Data Standards and statistical principles.

Unless otherwise specified, endpoints / variables defined in Section 11.1.1 will be summarised using descriptive statistics, graphically presented (where appropriate) and listed.

#### 11.1.5.1. Interim Analysis

No interim analyses are currently planned for this study.

#### 11.1.5.2. Statistical Methodology Specification

Endpoint / Variables

 
Average of systolic blood pressure (SBP) as measured by ambulatory blood pressure monitoring (ABPM) over 6-hr post-dosing after 8 weeks (i.e. Day 57) of Hgb maintenance therapy
 

Model Specification

 
ANCOVA with terms for treatment, prior ESA dose (low/high), and post-HD/pre-Acute Challenge 1 SBP, difference between post-HD/pre-Acute Challenge 2 SBP and post-HD/pre-Acute Challenge 1 SBP, and treatment by (difference in post-HD SBP between Acute Challenge 1 and 2) interaction. Note that the pre-challenge SBP may change over time between Acute Challenge 1 and Acute Challenge 2 as a result of the maintenance therapy, and thus the pre-challenge SBP at Acute Challenge 2 is not a true pre-treatment covariate. As a result, the interpretation of the effect of the Acute Challenge 2 may be confounded by the impact of treatment phase on the covariate. Therefore, if the interaction term in this model is significant at the 0.10 level, then the primary model will be ANCOVA with terms for treatment, prior ESA dose (low/high), and post-HD/pre-Acute Challenge 1 SBP.
 

Model Checking & Diagnostics

 
Distributional assumptions underlying the statistical analyses will be assessed by visual inspection of residual plots. Normality will be examined by normal probability plots, while homogeneity of variance
 

**CONFIDENTIAL**

205665

will be assessed by plotting the residuals against the predicted values for the model. If assumptions are grossly violated, alternative analyses will be considered.
Model Results Presentation

 
The point estimate, two-sided 95% CI and p-value for the difference between treatment groups will be presented from the selected final model for the superiority assessment. Superiority will be established if the p-value is <0.05.
 

Sensitivity and Supportive Analyses

 
If there are protocol deviations that are thought to potentially impact the primary endpoints (defined as at least 10% of the ITT population being excluded from the PP population), an exploratory sensitivity analysis will be completed. The analysis used for the primary endpoint will be repeated and similar results will be presented.
 
Participants who discontinue randomized study medication early will have their missing Day 57 AC2 ABPM data imputed; a sensitivity analysis will be run on the primary endpoint including these participants.
 
The primary endpoint will analyse using a 6-hour average of BP from ABPM device, sensitivity analyses using 8, 12, and 24-hour averages will be analysed using the primary model explained above in the model specification section.
 

**11.2. Secondary Pharmacodynamic Analyses****11.2.1. Endpoint / Variables**

Secondary Objectives	Secondary Endpoints

 
To compare the initial effect of daprodustat to epoetin alfa on BP after Acute Challenge 1 (2 weeks of erythropoiesis-stimulating agent [ESA] washout)
 
	
 
Average of SBP, diastolic blood pressure (DBP), mean arterial blood pressure (MAP), and heart rate (HR) as measured by ABPM over 6-hr post-dosing at Day 1
 
Area under the effect curve (AUEC) of SBP, DBP, MAP, and HR as measured by ABPM over 24-hr post-dosing at Day 1
 

 
To compare the effect of daprodustat to epoetin alfa on BP after Acute Challenge 2
 
	
 
Average of DBP, MAP, and HR as measured by ABPM over 6 hr post-dosing at Day 57.
 
AUEC of SBP, DBP, MAP, and HR as measured by ABPM over 24-hr post-dosing at Day 57.
 

 
To estimate the initial effect of daprodustat and epoetin alfa on SBP, DBP, HR and MAP after Acute Challenge 1 and 2
 
	
 
Change from pre-dose in SBP, DBP, HR, and MAP at each timepoint at Day 1 and Day 57
 

**11.2.2. Summary Measure**

Secondary Endpoints	Summary Measure

 
Average of SBP, diastolic blood pressure (DBP), mean arterial blood pressure (MAP), and heart rate (HR) as measured by ABPM over 6-hr post-dosing at Day 1
 
	
 
Average SBP, DBP, MAP, and HR over 6 hours post-dosing on Day 1
 
AUEC for SBP, DBP, MAP, and HR over 24 hours post-dosing on Day 1
 

CONFIDENTIAL

205665

Secondary Endpoints	Summary Measure

 
Area under the effect curve (AUEC) of SBP, DBP, MAP, and HR as measured by ABPM over 24-hr post-dosing at Day 1
 
	

 
Average of DBP, MAP, and HR as measured by ABPM over 6 hr post-dosing at Day 57.
 
AUEC of SBP, DBP, MAP, and HR as measured by ABPM over 24-hr post-dosing at Day 57.
 
	
 
Average DBP, MAP, and HR over 6 hours post-dosing on Day 57
 
AUEC for SBP, DBP, MAP, and HR over 24 hours post-dosing on Day 57
 

 
Change from pre-dose in SBP, DBP, HR, and MAP at each timepoint at Day 1 and Day 57
 
	
 
Mean change in SBP, DBP, HR, and MAP at each timepoint on Day 1 and Day 57
 

### 11.2.3. Population of Interest

The secondary pharmacodynamics analyses will be based on the ITT population, unless otherwise specified.

### 11.2.4. Strategy for Intercurrent (Post-Randomization) Events

If the primary sensitivity analysis for missing data differs with the primary endpoint, further sensitivity analyses on the secondary endpoints will be analysed. These potential, additional sensitivity analyses will follow how the primary endpoint sensitivity analysis was analysed, see Section 11.1.4 and Section 14.6.6 for details.

### 11.2.5. Statistical Analyses / Methods

Details of the planned displays are provided in [Appendix 12: List of Data Displays](#) and will be based on GSK Data Standards and statistical principles.

Unless otherwise specified, endpoints / variables defined in Section 11.2.1 will be summarised using descriptive statistics, graphically presented (where appropriate) and listed.

#### 11.2.5.1. Statistical Methodology Specification

Endpoint / Variables

 
Average of SBP, DBP, HR, and MAP
 
AUEC of SBP, DBP, HR, and MAP
 
Change from pre-dose in SBP, DBP, HR, and MAP at each timepoint at Day 1 and Day 57
 

Model Specification

 
For the first secondary endpoint, Average SBP over 6 hr post-dose in Acute Challenge 1 will be analyzed using ANCOVA with terms for treatment, prior ESA dose (low/high), and post-HD/pre-Acute Challenge 1 SBP. Similar analyses will be performed for DBP, MAP, and HR.
 
ANCOVA using the primary model will be used for the analysis of average DBP, MAP, and HR over 6 hr post-dose in Acute Challenge 2 replacing SBP terms with the analogous measurement for DBP, MAP, and HR respectively. 
 
ANCOVA with terms for treatment, prior ESA dose (low/high), and post-HD/pre-Acute Challenge 1 ABPM (DBP/MAP/HR), difference between post-HD/pre-Acute Challenge 2 ABPM (DBP/MAP/HR) and post-HD/pre-Acute Challenge 1 ABPM (DBP/MAP/HR), and treatment by (difference in post-HD ABPM (DBP/MAP/HR) between Acute
 
 
 

**CONFIDENTIAL**

205665

Challenge 1 and 2) interaction. Note that the pre-challenge ABPM (DBP/MAP/HR) may change over time between Acute Challenge 1 and Acute Challenge 2 as a result of the maintenance therapy, and thus the pre-challenge ABPM (DBP/MAP/HR) at Acute Challenge 2 is not a true pre-treatment covariate. As a result, the interpretation of the effect of the Acute Challenge 2 may be confounded by the impact of treatment phase on the covariate. Therefore, if the interaction term in this model is significant at the 0.10 level, then the primary model will be ANCOVA with terms for treatment, prior ESA dose (low/high), and post-HD/pre-Acute Challenge 1 ABPM (DBP/MAP/HR).
 
 
For the second secondary endpoint, AUEC of SBP, DBP, HR, and MAP post-acute challenge 1 and 2 will be analyzed using an ANCOVA model with terms for treatment and prior ESA dose (low/high).
 
The AUEC for ABPM will only be analysed if a subject has ABPM data up to hour 24. 
 
For example if the subject has ABPM data up to hour 23, the subject will be excluded from the ABPM AUEC analysis.
 
If more than 25% of subjects are excluded from the ABPM AUEC analysis because the subject is missing any of the 3 possible hour 24 ABPM measurements, then an extrapolation technique of average hour 23 measurement carried forward to hour 24 may be utilized as a sensitivity analysis for AUEC ABPM.
 
 
 

Model Checking & Diagnostics
 
 
Distributional assumptions underlying the statistical analyses will be assessed by visual inspection of residual plots. Normality will be examined by normal probability plots, while homogeneity of variance will be assessed by plotting the residuals against the predicted values for the model. If assumptions are grossly violated, alternative analyses will be considered.
 
Section 14.6.6 outlines any transformation of data as needed.
 


Model Results Presentation
 
 
The point estimate, two-sided 95% CI and p-value for the difference between treatment groups will be presented from all ANCOVA models for the superiority assessment. Superiority will be established if the p-value is <0.05.
 
Plot of hourly average ABPM will be created for SBP, DBP, MAP, and HR for both AC1 and AC2.
 
Change from pre-dose in SBP, DBP, HR, and MAP at each timepoint at Day 1 and Day 57 will be summarized in a table.
 

Sensitivity and Supportive Analyses
 
 
If more than 25% of subjects are excluded from the ABPM AUEC analysis because the subject is missing any of the 3 possible hour 24 ABPM measurements, then an extrapolation technique of average hour 23 measurement carried forward to hour 24 may be utilized as a sensitivity analysis for AUEC ABPM. 
 
This will be only for the AC2 SBP, other sensitivity analyses may be considered.
 
 
 

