9.4.2. Secondary Analyses

Average SBP over 6 hr post-dose in Acute Challenge 1 will be analyzed using ANCOVA with terms for treatment, prior ESA dose (low/high), and post-HD/pre-Acute Challenge 1 SBP. Similar analyses will be performed for DBP, MAP, and HR.

ANCOVA using the primary model will be used for the analysis of average DBP, MAP, and HR over 6 hr post-dose in Acute Challenge 2 replacing the baseline SBP term with the analogous baseline measurement for DBP, MAP, and HR respectively.

AUECs of SBP, DBP, MAP, and HR post Acute Challenge 2 and 1 will be analyzed using ANCOVA with terms for treatment and prior ESA dose (low/high) with 95% CIs and p-values provided for the treatment effect.

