### 5.4. Examination of Covariates, Other Strata and Subgroups

#### 5.4.1. Covariates and Other Strata

The list of covariates and other strata may be used in descriptive summaries and statistical analyses, some of which may also be used for subgroup analyses. Additional covariates and other strata of clinical interest may also be considered.

Category	Details
Strata	Prior treatment by ESA Dose (low ESA/high ESA)
Covariates	Treatment (daprodustat/epoetin alfa)
	Post_HD/pre-Acute Challenge 1 BP (SBP, DBP, MAP, HR)
	Difference in SBP between post-HD/pre-Acute Challenge 2 BP (SBP, DBP, MAP, HR) and post-HD/pre-Acute Challenge 1.

The pre-challenge SBP may change over time between Acute Challenge 1 and Acute Challenge 2 as a result of the maintenance therapy, and thus the pre-challenge SBP at Acute Challenge 2 is not a true pre-treatment covariate. Therefore, pre-Acute Challenge 2 SBP will not be used as a covariate. Instead, any impact on the SBP due to the covariate between Challenge 1 to Challenge 2 will be adjusted for using the covariate ‘Difference in SBP between post-HD/pre-Acute Challenge 2 SBP and post-HD/pre-Acute Challenge 1’.

The primary model will include the interaction between treatment and ‘difference in post-HD SBP between Acute Challenge 1 and 2’. As a result, the interpretation of the effect of the Acute Challenge 2 may be confounded by the impact of treatment phase on the covariate. Therefore, if the interaction term in this model is significant at the 0.10 level, then the primary model will be ANCOVA with terms for treatment, post-HD/pre-Acute Challenge 1 SBP, and prior ESA dose (low/high).

Stratification factor (previous ESA dose) will be used as a fixed factor in the model where indicated in Section 11. See details below:

Classification Name (Description)	Value	Code/Range
Treatment by ESA Dose (Treatment by Previous ESA Dose)	Low ESA Dose	1
	High ESA Dose	2

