**CONFIDENTIAL**

205665

each acute challenge. Cmax, tmax, AUC(0-24), baseline adjusted AUC and baseline adjusted Cmax will all be summarized by treatment arm and for each acute challenge day.
 
 
• Change in AUEC of SBP from Day 57 to Day 1 for each treatment arm will be summarized in a table.
 
• The difference in SBP between pre-dose in Acute Challenge 1 and pre-dose in Acute Challenge 2 will be summarized by treatment group. Similar summaries of DBP, MAP, and HR will be performed.
 
• For each acute challenge, change from pre-challenge in SBP, DBP, MAP, and HR will be summarized by treatment group at each timepoint. In addition, for each acute challenge, SBP, DBP, MAP, and HR will be summarized by treatment group at each timepoint. Line graphs of this information will be provided by treatment group for each acute challenge.
 
• For the following endpoints, an ANCOVA model will be used with terms for baseline SBP, treatment, and prior ESA dose (low/high): 
 
○ Change in SBP from pre-dose on Day 1 to Cmax of the study treatment on Day 1, as measured by ABPM
 
○ Change in SBP from pre-dose on Day 57 to Cmax of the study treatment on Day 1, as measured by ABPM
 
○ Change in SBP from pre-dose on Day 57 to Cmax of the study treatment on Day 57, as measured by ABPM
 
○ Change in SBP from pre-dose on Day 1 to Cmax of erythropoietin on Day 1, as measured by ABPM
 
○ Change in SBP from pre-dose on Day 57 to Cmax of erythropoietin on Day 1, as measured by ABPM
 
○ Change in SBP from pre-dose on Day 57 to Cmax of erythropoietin on Day 57, as measured by ABPM
 
 
 

Model Checking & Diagnostics
 
 
• Distributional assumptions underlying the statistical analyses will be assessed by visual inspection of residual plots. Normality will be examined by normal probability plots, while homogeneity of variance will be assessed by plotting the residuals against the predicted values for the model. If assumptions are grossly violated, alternative analyses will be considered.
 

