## CONFIDENTIAL

205665

Pharmacodynamic and Biomarker					
= post-HD/pre- Acute challenge 2– post-HD/pre-Acute challenge 1					

 
This applies for SBP, DBP, HR, and MAP
 
					
AUEC Secondary Endpoints					

 
Baseline, or time zero, for AUEC of ABPM data will be defined as the first ABPM measurement. If the first ABPM measurement is missing or excluded, then BP data from vitals will be used.               
 
For these subjects, if the recorded time of vitals measurement is > 24 hours before the last ABPM measurement, then last ABPM measurement time is used in place of baseline time.
 
 
 
AUEC will be calculated using the linear trapezoidal rule for each incremental trapezoid and the log trapezoidal rule for each decremental trapezoid.
 
AUEC timepoints will be converted to be on the hourly scale               
 
For example, if the second measurement is listed as 00:15, then this will be converted to the hourly scale of 0.25
 
 
 
The AUEC for ABPM will only be analysed if a subject has ABPM data up to hour 24.               
 
For example if the subject has ABPM data up to hour 23, the subject will be excluded from the ABPM AUEC analysis.
 
If more than 25% of subjects are excluded from the ABPM AUEC analysis because the subject is missing any of the 3 possible hour 24 ABPM measurements, then an extrapolation technique of average hour 23 measurement carried forward to hour 24 may be utilized as a sensitivity analysis for AUEC ABPM.
 
 
 
If the AUEC data appears to be skewed, then the data will be log-transformed. Instead of reporting mean and standard deviation, the geometric mean and CV will be reported
 
					
Change from pre-dose in SBP, DBP, HR, and MAP at each timepoint at Day 1					

 
Each timepoint is defined as every 15 minutes for the first 6 hours, then every 20 minutes after.
 
The first measurement will be defined as pre-acute challenge and will not be used when calculating the averages.
 
The calculation will look like the following:               
 
Change = Measurement – Pre-acute challenge measurement
 
 
 
					

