## CONFIDENTIAL

205665

Pharmacodynamic and Biomarker: Tables					
No.	Population	IDSL / Example Shell	Title	Programming Notes	Deliverable
4.37.	ITT	PDT8	Summary of Analysis of Average 6hr ABPM SBP post-AC2, Imputed Data	Use imputed missing values for AC2 for early withdrawal subjects, calculate 6hr averages for those subjects who failed QC for any AC.  For subjects who AC2 failed QC, 6hr average SBP will be calculated without imputation	DR, SAC
4.38.	ITT	PDT3	Summary of Analysis of Average 8hr ABPM SBP post-AC2		DR, SAC
4.39.	ITT	PDT3	Summary of Analysis of Average 12hr ABPM SBP post-AC2		DR, SAC
4.40.	ITT	PDT3	Summary of Analysis of Average 24hr ABPM SBP post-AC2		DR, SAC
4.41.	ITT	PDT4	Summary of Analysis of AUEC SBP over 24hr post-AC2, Imputed Data	
 
If more than 25% of subjects are excluded from the ABPM AUEC analysis then this sensitivity analysis will be performed for the AC2 SBP AUEC model               
 
If during dry-run less than 25% of subjects are excluded, then table is not needed for dry-run
 
 
 
	SAC
Additional PD tables					
4.42.	ITT	PDT10	Summary of Subjects who QC Pass Acute Challenges	Column by treatment, row by Day 1 and Day 57, where Day 57 includes repeat AC2	SAC

CONFIDENTIAL

205665

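### The eight 24-hour AUEC models omit the pre-challenge baseline that the plan's other blood pressure and heart rate ANCOVAs carry, at a cost in precision

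*SAP*

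**What the plan says.** Protocol 9.4.2 states that the AUECs of SBP, DBP, MAP and HR after both challenges "will be analyzed using ANCOVA with terms for treatment and prior ESA dose (low/high) with 95% CIs". SAP 11.2.5.1 repeats this: the AUEC "will be analyzed using an ANCOVA model with terms for treatment and prior ESA dose (low/high". Four parameters at two challenges make eight models (SAP Tables 4.13 to 4.20). SAP 14.6.6 derives the AUEC by the trapezoidal rule from the time-zero reading onward and does not subtract baseline; the baseline-corrected area defined there is for biomarkers only.

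The plan treats its other blood pressure and heart rate comparisons differently:

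- The primary model and its fallback (SAP 11.1.5.2) both contain pre-Acute Challenge 1 SBP.
- The 6-hour average at Acute Challenge 1 uses "ANCOVA with terms for treatment, prior ESA dose (low/high), and post-HD/pre-Acute Challenge 1 SBP", with similar models for DBP, MAP and HR (SAP 11.2.5.1). The 6-hour DBP, MAP and HR averages at Acute Challenge 2 follow the primary model.
- For longer averages of SBP after Acute Challenge 2, "sensitivity analyses using 8, 12, and 24-hour averages will be analysed using the primary model explained above in the model specification section" (SAP 11.1.5.2). Table 4.40 is titled "Summary of Analysis of Average 24hr ABPM SBP post-AC2".
- For the SBP changes at the time of Cmax, "an ANCOVA model will be used with terms for baseline SBP, treatment, and prior ESA dose (low/high" (SAP 11.3.1.1).
- The multiple-imputation analysis (SAP 14.6.6) reuses the primary model.

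SAP 5.4.1 already lists "Post_HD/pre-Acute Challenge 1 BP (SBP, DBP, MAP, HR" among the covariates.

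**The concern.** A patient with high pressure before the challenge will tend to have a large 24-hour area whichever drug is given. Without a baseline term, that between-patient variation goes into the residual and widens the interval for the treatment difference.

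The clearest sign that this is an oversight is at Acute Challenge 2. The 24-hour average SBP (Table 4.40) and the SBP AUEC (Table 4.17) summarise nearly the same readings, yet one is baseline-adjusted and the other is not. Table 4.40 covers that single case. The other seven AUEC comparisons (all four at Acute Challenge 1; DBP, MAP and HR at Acute Challenge 2) have no adjusted 24-hour counterpart.

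At stake are eight pre-specified comparisons, each reported with an estimate, a 95% CI and a p-value. SAP 5.5 calls secondary tests exploratory, although SAP 11.2.5.1 still attaches a superiority rule at p < 0.05 to all these ANCOVAs.

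**Working it through.** **Inputs.** From protocol 9.2.1, 9.2.2 and Tables 6 and 7: two-sided 5% level; SD 16 mmHg (range 14 to 20) and a 15 mmHg difference, both for 6-hour average SBP; 31 per arm at Acute Challenge 1 and 25 at Acute Challenge 2. The documents give no SD or effect for the AUEC or for a 24-hour mean, so the mmHg figures below borrow the 6-hour values as an illustration. The correlation r between the pre-challenge value and the outcome is not given either; 0, 0.3, 0.5 and 0.7 are assumed.

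**Is AUEC/24 close to the 24-hour average?** The time-zero reading enters the AUEC but not the average. With a 15-minute first interval its weight is 0.125/24 = 0.5%. The two are nearly the same quantity.

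**Reproducing the plan.** Unadjusted half-width = t(0.975, 2n−2) × SD × √(2/n).

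- 25 per arm: 2.0106 × 16 × √0.08 = 9.10 mmHg; noncentral-t power for 15 mmHg is 90%.
- 31 per arm: 2.0003 × 16 × √(2/31) = 8.13 mmHg; power 95%.

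Both match Table 6 (9.1 and 8.1 mmHg; 90% and 95%).

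**With the baseline term.** Adjusted half-width = t(0.975, 2n−3) × SD × √(1−r²) × √[(2/n)(1 + 1/(2n−4))]. The last factor is the expected price of chance baseline imbalance. For r = 0.5 and 25 per arm: 2.0117 × 16 × 0.8660 × √(0.08 × 47/46) = 7.97 mmHg. Including the ESA stratum term changes half-widths by about 0.01 mmHg.

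| r (assumed) | Width ratio, 25/arm | Half-width, 25/arm | Power for 15 mmHg, 25/arm | Half-width, 31/arm |
|---|---|---|---|---|
| As planned | 1 | 9.10 | 90% | 8.13 |
| 0 | 1.01 | 9.20 | 89% | 8.20 |
| 0.3 | 0.96 | 8.78 | 92% | 7.82 |
| 0.5 | 0.88 | 7.97 | 96% | 7.10 |
| 0.7 | 0.72 | 6.57 | 99% | 5.86 |

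The width ratio depends only on r and n, so it carries over to DBP, MAP and HR. The mmHg and power columns do not.

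**Break-even.** Adjustment helps once √(1−r²) is below 1 divided by the r = 0 ratio. At 25 per arm that is r > √(1 − 1/1.0114²) = 0.15; at 31 per arm, r > √(1 − 1/1.0089²) = 0.13.

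**Other conditions.** At r = 0.5 and 25 per arm, for SD 14, 16, 18 and 20, power moves from 96, 90, 82 and 74% to 99, 96, 91 and 84%. The AUEC set is limited to patients with data to hour 24. If that removed a quarter of them (assumed; 25 × 0.75 ≈ 19 per arm), 80% power would become 83, 89 or 97% at r = 0.3, 0.5 or 0.7.

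**Simulation check** (treatment, stratum and baseline terms; SD 16; 25 per arm; 10,000 runs per setting). Mean half-width was 9.07 mmHg unadjusted and 8.76, 7.93 and 6.54 adjusted at r = 0.3, 0.5 and 0.7. Type I error was 4.8 to 5.1% for both models. A separate run at 31 per arm found no bias in the unadjusted estimate with complete data, or with baseline-dependent dropout alike in both arms. With about 19% dropout that depended on baseline in one arm only, a hypothetical case, the unadjusted estimate was off by 1.3 to 2.3 mmHg and the adjusted one by about zero.

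**The case against.** The two-term model is valid, protocol and SAP agree on it, and Amendment 4 reopened these models and added only the stratification term. All of that stands. The point is an unexplained inefficiency, not an error or a conflict between documents.

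The size of the gain rests on an r that the plan does not give. The covariate is a single reading, which SAP 14.6.6 allows to be replaced by a vital-signs value or, if Day 1 is missing, by a Week -2 or screening value. At Acute Challenge 2 it is eight weeks old, and protocol 6.11.1 lets patients stay in after antihypertensive changes. So r may be low, especially at Acute Challenge 2, and at r = 0.3 the gain is small. This limits the size but not the direction: the downside at r = 0 is about 1%.

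Table 4.40 is not simply the AUEC model plus a baseline. It uses the primary model, which by default also conditions on the change in pre-challenge SBP and its interaction with treatment, and no hour-24 rule is stated for it. That is correct, and it argues for adding only the pre-Challenge 1 value.

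The plan also has descriptive change-from-pre-dose tables (4.21 to 4.24) and baseline-adjusted 6-hour comparisons. Neither replaces an adjusted 24-hour comparison.

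Finally, changing eight protocol-stated models in an open-label study could look data-driven. A change documented before database release answers that.

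**Conclusion.** The concern holds as a precision point of modest size. All eight AUEC models leave out a baseline value that is already collected, already listed as a covariate and used in the plan's other blood pressure and heart rate ANCOVAs. The conditional AUEC sensitivity analysis (Table 4.41) appears to share the omission.

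No confirmatory conclusion depends on this. The intervals are valid but probably wider than they need be: by the assumed r, adjustment would bring them to between 1.01 (r = 0) and 0.72 (r = 0.7) of their present width at 25 per arm. Only the direction, for r above about 0.15, is secure. The amount rests on an assumed r, and the mmHg and power figures also rest on the 6-hour SD and effect.

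**What to change.** Before database release, add the post-dialysis, pre-Acute Challenge 1 value of the same parameter (SBP, DBP, MAP or HR) to each of the eight AUEC models and to the Table 4.41 analysis. Use the pre-Challenge 1 value at both challenges. The pre-Challenge 2 value should stay out, because the plan itself says maintenance treatment may have changed it. SAP 14.6.6 provides that "If the AUEC data appears to be skewed, then the data will be log-transformed"; in that case log-transform the covariate as well. Record the change in SAP Table 1, since protocol 9.4.2 states the two-term model.

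The cost is one model term, one degree of freedom and one line in SAP Table 1, with no new data. The primary model and the other 6-hour models at Acute Challenge 2 already need the same pre-Challenge 1 value. The AUEC model at Acute Challenge 2 would still differ from the primary model, which also has the pre-challenge difference and its interaction with treatment.

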#### 5.5. Multiple Comparisons and Multiplicity

No multiplicity adjustments will be made for the final analysis of the secondary endpoints. Although the secondary and exploratory analyses will include statistical testing, these will be considered as exploratory and no Type I error adjustments will be made.

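### SAP 11.2.5.1 sets a superiority rule at p<0.05 for all 15 secondary ANCOVAs, which conflicts with SAP 5.5, where the same tests are exploratory and unadjusted

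*SAP*

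**What the plan says.** SAP 11.2.5.1, under Model Results Presentation, deals with the secondary ANCOVAs. "The point estimate, two-sided 95% CI and p-value for the difference between treatment groups" are to be "presented from all ANCOVA models for the superiority assessment", and superiority is taken as established at p<0.05. This is the decision rule that SAP 11.1.5.2 gives for the primary endpoint. No sentence makes a secondary claim depend on the primary result, and none says which direction counts as superior.

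The models it covers are set out in the same section:
- 6-hour averages in Acute Challenge 1: an SBP model, and "Similar analyses will be performed for DBP, MAP, and HR".
- 6-hour averages in Acute Challenge 2: "ANCOVA using the primary model will be used for the analysis of average DBP, MAP, and HR over 6 hr post-dose in Acute Challenge 2".
- 24-hour curves: "AUEC of SBP, DBP, HR, and MAP post-acute challenge 1 and 2 will be analyzed using an ANCOVA model".

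SAP 5.5 takes a different position: "No multiplicity adjustments will be made for the final analysis of the secondary endpoints". It adds that although secondary and exploratory analyses include testing, "these will be considered as exploratory and no Type I error adjustments will be made".

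**The concern.** A test treated as exploratory yields an estimate, an interval and a descriptive p-value. A rule that establishes superiority yields a claim. The SAP gives both descriptions to the same 15 tests. An author who drafts the report from the methods section could write that superiority was established on a diastolic, MAP, heart rate or AUEC endpoint, even after a non-significant primary result, and cite the SAP for it. An author who starts from 5.5 would not. For heart rate the SAP does not say what superiority would mean, because the p-value is two-sided and no favourable direction is given.

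**Working it through.** **The texts side by side**

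| Place | Tests covered | Superiority rule? |
|---|---|---|
| Protocol 9.4.1; SAP 11.1.5.2 | Primary endpoint | Yes, p<0.05 |
| Protocol 9.4.2 | Secondary | None stated; AUECs get 95% CIs and p-values |
| SAP 5.5 | Secondary and exploratory | Exploratory, no adjustment |
| SAP 11.2.5.1 | Secondary | Yes, p<0.05, all ANCOVAs |
| SAP 11.3.1.1 | Exploratory | None; estimate, CI and p-value only |

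The formal hypotheses in Protocol 9.1 and SAP 2.4 concern only the primary endpoint. SAP Table 1, which lists changes from the protocol's analysis plan, does not mention a superiority rule for secondary endpoints.

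**Number of tests**

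- 6-hour averages, Acute Challenge 1: SBP, DBP, MAP, HR = 4
- 6-hour averages, Acute Challenge 2: DBP, MAP, HR = 3 (SBP is the primary)
- 24-hour AUEC: 4 parameters × 2 challenges = 8

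4 + 3 + 8 = 15, which matches Tables 4.6 to 4.20 (20 − 6 + 1 = 15). The change-from-pre-dose endpoint is only summarised, so it is not counted.

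**Chance of at least one p<0.05 if no endpoint has a true effect**

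The documents give no familywise figure to reproduce, and no correlations between endpoints.

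Under independence: 1 − 0.95^15 = 0.537 in either direction, and 1 − 0.975^15 = 0.316 in one direction. The expected number of false positives is 15 × 0.05 = 0.75, whatever the correlation.

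For correlated tests, take 15 standard normal statistics Z_i = √ρ·U + √(1−ρ)·e_i, with U and the e_i independent standard normals. Count how often any |Z_i| exceeds 1.96, or how often any Z_i falls below −1.96 for one direction. Results from 400,000 draws for each ρ:

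| Assumed common ρ | Either direction | Favouring daprodustat only |
|---|---|---|
| 0.5 | 36.1% | 18.1% |
| 0.7 | 25.6% | 12.7% |
| 0.8 | 20.3% | 10.1% |
| 0.9 | 14.3% | 7.1% |

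The last column needs one direction per endpoint to be called favourable, which the SAP does not do.

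A single common ρ is a simplification, because heart rate need not follow pressure closely. Three structured patterns were therefore also assumed. In each, MAP is built as (SBP + 2·DBP)/3, and correlations are set for SBP with DBP, pressure with HR, between challenges, and between the two summaries:
- 0.5, 0, 0.3, 0.6: 39.5%
- 0.7, 0, 0.5, 0.8: 32.6%
- 0.8, 0.2, 0.7, 0.9: 26.2%

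All three are for either direction.

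**The case against.** The best defence is that the two sections can be read together. SAP 5.5 is the dedicated multiplicity section, it foresees that secondary endpoints will be tested, and it says how those tests are to be regarded. On that reading 11.2.5.1 only supplies the nominal threshold, and 5.5 tells the reader how little weight it carries. Nothing in the SAP ranks 11.2.5.1 above 5.5, so a reader who infers that a superiority claim is already built into the plan goes too far. The text permits the claim; it does not require it. This part of the defence stands.

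It does not remove the conflict. SAP 11.3.1.1 uses nearly the same presentation sentence for the exploratory ANCOVAs and stops before any superiority rule. If the secondary tests have the same exploratory status, the extra sentence in 11.2.5.1 has no role except to authorise a claim.

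A second defence is that Protocol 9.4.2 reuses the primary model for the Acute Challenge 2 averages, and so might carry its superiority rule with it. That could reach three tests at most. It does not reach the four Acute Challenge 1 averages or the eight AUEC analyses.

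A third defence concerns size. A reader might take 54% as the false-claim rate. That figure requires independence, which does not hold: MAP depends on SBP and DBP, the 6-hour averages overlap the 24-hour AUECs, and both challenges are measured in the same subjects. It is an upper reference only. If the worry is a false claim for daprodustat, one tail is the relevant count and the figures roughly halve. Both points stand and are reflected in the ranges given.

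**Conclusion.** The conflict is real and should be corrected. SAP 11.2.5.1 sets a superiority decision rule for 15 secondary tests, with no dependence on the primary and no direction, while SAP 5.5 treats them as exploratory and the protocol's secondary analysis section states no such rule.

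Its scope is limited. A reader might infer that the trial's Type I error is inflated or that the multiplicity is concealed. The documents support neither. The primary is one comparison on one endpoint at 0.05, no secondary result can replace or alter it, and 5.5 states openly that nothing is adjusted. The dispute is over what the report may claim.

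On size, with no true effects, the chance of at least one p<0.05 in either direction is about 36% at an assumed common correlation of 0.5, falling to 14% at 0.9 (18% to 7% for results favouring daprodustat only). The structured patterns gave 26% to 39% in either direction. All the correlations are assumptions. Even at 0.9 the two-sided figure is nearly three times 5%.

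**What to change.** In SAP 11.2.5.1, Model Results Presentation, delete the words that tie the secondary results to a superiority assessment and the sentence after them that establishes superiority at p<0.05. Report point estimates, 95% CIs and p-values labelled as nominal, in line with SAP 11.3.1.1. Add a sentence in 5.5 or 11.2.5.1 that superiority is assessed only for the primary endpoint.

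The cost is SAP wording. No model, table, sample size or data collection changes. The sponsor gives up superiority language on secondary endpoints, which is where 5.5 already leaves it. If the sponsor wants to keep such claims, it needs a prespecified procedure instead, such as a fixed sequence after the primary, or Bonferroni at 0.05/15 = 0.0033 per test.
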